8.2 Serious adverse events

An SAE is defined as any adverse event [appearance of (or worsening of any pre-existing)], undesirable sign(s), symptom(s) or medical conditions(s) which meets any one of the following criteria:

- fatal
- life-threatening. Life-threatening in the context of a SAE refers to a reaction in which the subject was at risk of death at the time of the reaction; it does not refer to a reaction that hypothetically might have caused death if it were more severe
- results in persistent or significant disability/incapacity
- constitutes a congenital anomaly/birth defect
- requires inpatient hospitalization or prolongation of existing hospitalization, unless hospitalization is for:
 - routine treatment or monitoring of the studied indication, not associated with any deterioration in condition
 - elective or pre-planned treatment for a pre-existing condition that is unrelated to the indication under study and has not worsened since signing the informed consent
 - social reasons and respite care in the absence of any deterioration in the subject's general condition
 - treatment on an emergency outpatient basis for an event not fulfilling any of the definitions of a SAE given above and not resulting in hospital admission
- is medically significant, e.g. defined as an event that jeopardizes the subject or may require medical or surgical intervention to prevent one of the outcomes listed above

Medical and scientific judgment should be exercised in deciding whether other situations should be considered serious reactions, such as important medical events that might not be immediately life threatening or result in death or hospitalization but might jeopardize the subject or might require intervention to prevent one of the other outcomes listed above. Such events should be considered as "medically significant". Examples of such events are intensive treatment in an emergency room or at home for allergic bronchospasm, blood dyscrasias or convulsions that do not result in hospitalization or development of dependency or abuse (please refer to the ICHE2D Guidelines).

8.3 SAE reporting

To ensure subject safety, every SAE, regardless of causality, occurring after the subject has provided informed consent and until 10 weeks following the last administration of study dressings must be reported within 24 hours of learning of its occurrence.

All follow-up information for the SAE including information on complications, progression of the initial SAE and recurrent episodes must be reported as follow-up to the original episode within 24 hours of the investigator receiving the follow-up information. An SAE occurring at a different time interval or otherwise considered

completely unrelated to a previously reported one must be reported separately as a new event.

If the SAE is not previously documented (new occurrence) and is thought to be related to the study treatment, a CMO & PS Department associate may urgently require further information from the investigator for health authority reporting.

Suspected Unexpected Serious Adverse Reactions (SUSARs) will be collected and reported to the competent authorities and relevant ethics committees in accordance with EU Guidance 2011/C 172/01 or as per national regulatory requirements in participating countries. Any SAEs experienced after the 10 week period following the last administration of study treatment should only be reported if the investigator suspects a causal relationship to study treatment. Any SAEs reported up to the subject's last visit will be reported in the AE eCRF. SAEs beyond that date will only be recorded in the Safety database.

Risks to subjects in this study include contact dermatitis in the skin areas exposed to the dressings provided in this study. However, we will be utilizing FDA-cleared dressings that are available on the market and therefore pose a risk that is no higher than the current risk subjects are undertaking while utilizing other dressings over the same skin areas.

8) Potential Benefits to Subjects*

Direct benefits to subjects include complimentary access to various high quality dressings that they might otherwise not have had access to as they may not be covered by insurance for HS.

9) Vulnerable Populations*

Pregnant women, prisoners, and children younger than 18 years old are excluded.

10) Setting

Patients will be recruited from outpatient dermatology clinics and wound centers at the University of Miami Clinics and Hospital at [name]. Subjects will be offered follow up at outpatient dermatology research offices located at the University of Miami Hospital West Building, [name]. All of the necessary procedures for the study will take place at this location.

11) Resources Available

[name]., is a dermatologist with expertise in wound healing disorders including Hidradenitis Suppurativa; he will be the primary investigator on this study. All subjects will be recruited from outpatient dermatology clinics and wound centers and he can perform detailed wound and skin evaluations.

All associated study personnel are CITI certified and have extensive data analysis training.

12) Prior Approvals

None.

13) Recruitment Methods

Thirty subjects (30) with a diagnosis of Hidradenitis Suppurativa will be recruited by the Investigator and study staff. Subjects will be recruited from outpatient dermatology clinics and the Wound Care Center at the University of Miami. During their standard visit, subjects will be offered the opportunity to enroll in the study. If subjects agree to take part in this study, study staff will guide subjects through the informed consent process.

Subjects will be asked to sign the informed consent form and the photo consent form before the study procedures begin. Subjects will be given ample time to consider the study and all questions will be answered by study staff. Subjects will be enrolled from the date of protocol approval for a 12 months period.

14) Local Number of Subjects

This is a pilot study for which we intend to reach 20 subjects. We anticipate a high drop-out rate, and therefore intend to recruit and enroll a total of 30 subjects locally.

15) Confidentiality

The camera will be stored in a locked office in [name] until the end of the recruitment. The collected coded and encrypted images will be stored in the computers found at the research office protected by a password. The collected coded dressing logs will be stored at the research office in a locked cabinet. Both the encrypted images and the dressing logs will be securely stored for at least 3 years after the research project has concluded. Please see section 7 ('Data

Management') for more details on data coding and storage. Only the primary investigator and co-investigators will have access to the images, camera, and subject information.

16) Provisions to Protect the Privacy Interests of Subjects

All study records will be stored a password-protected computer, in a locked room. A separate datasheet will be created that will tabulate patients' names, MRN, date of birth and assign a subject ID. This subject ID will act as a code during the 6 weeks the subject is actively participating in the study. A second datasheet will contain only the subject ID and study relevant data. This will effectively create a de-identified database that will be used for analysis at the end of the study.

17) Consent Process

Consent will be obtained by a member of the study team in writing and will take place in outpatient dermatology clinics and wound centers after the subject completed their clinic visit. In the clinic, study staff will guide the subjects through the consent process. Study staff will describe the study and the procedures involved to the subject and review the potential risks and benefits. The subject will be given ample time to consider the study. Once the subject agrees to participate, an Informed Consent Form will be signed.

18) Process to Document Consent in Writing

Attached.

NOTE: IT IS UNCLEAR WHETHER YOU WILL NEED A PARTIAL WAIVER OF HIPAA FOR RECRUITMENT PURPOSES. IF YOU NEED IT, YOU NEED TO ADD THE FOLLOWING:

19) Authorization for Use and Disclosure of Protected Health Information (HIPAA)

If the research team will access patient medical records or other identifiable health information for this research, you must obtain a waiver of the requirement for written authorization from the patients to access their medical records.

Confirm that you will destroy or de-identify the information you collect at the earliest opportunity. ***I confirm***

Confirm that the information you collect will not be reused or disclosed to any other person or entity, except as required by law, for authorized oversight of the research study or for other research for which the use or disclosure of PHI is permissible.

I confirm

References

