We will additionally study how the usage of antimicrobial dressings will have an effect on the wound microbiome in order to see how this affects healing in the setting of HS. The presence of bacteria in the wound bed will be determined by analyzing the collected wound swab samples. Standard molecular techniques will be utilized for bacterial analysis. The purpose of collecting swab samples is purely qualitative in its intent to gather data on bio-bioburden and microbiome composition. Ulcer swab results are not indicated for therapeutic treatment nor diagnosis of infection. The results of sample swabs will not have an impact on the treatment plan for each participant.

3) Inclusion and Exclusion Criteria*

Inclusion criteria:

- Men and women ≥ 18 years of age
- Diagnosed with Hidradenitis Suppurativa (all stages of disease) by Dermatologist
- Presence of at least one lesion with active drainage
- Willing and able to provide informed consent

Exclusion criteria:

- Subjects younger than 18-years-old.
- Prisoners
- Pregnant or lactating women
- Adults unable to consent

4) Procedures Involved*

Study duration:

Each subject will have three visits total over a 6-week period.

Recruitment and procedures:

Participants recruited for this study will be patients at University of Miami Hospital (UMH) outpatient dermatology clinics and wound care centers, who present to UMH with a diagnosis of Hidradenitis Suppurativa (HS). During their office visit, patients will be invited to participate in a six-week study to determine which dressings are best suited for patients with HS.

Potential subjects will be informed of the study during their standard of care appointment and then asked if they would like to participate. After signing informed consent, a physical exam will be performed and information on the subjects' demographics, and medical history will be collected (visit 0). Quality of life will be assessed with DLQI instrument. Maximal and average pain will be assessed on a 5-

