point likert scale. Quality of sleep, drainage, and odor will be assessed as well (Table 1). Photographs and measurements will be taken of wounds associated with HS. Any active wounds will receive standard of care, including cleaning and debridement to remove all nonviable soft tissue from the wound by scalpel, tissue nippers and/or curettes when appropriate. Wound swab samples will be collected from patients from one active wound at each visit. This site will be identified during the baseline visit. If debridement is indicated as part of standard care, prior to debridement of the wound, a wound swab sample will be collected from the wound bed. In circumstances where a layer of nonviable tissue is preventing swab collection, the swab sample should be collected during the course of the debridement process wherein the wound bed has been exposed. Subjects will be provided with a kit that will include 3 types of FDA-cleared dressings (1) Cutimed® Sorbact® Hydroactive B, 2) Cutimed® Siltec®, and, 3) Sorbion® Sana multi-star) that are available on the market and general wound care supplies (i.e. tape, gauze) that are also FDA-cleared and available on the market. Dressing instructions involve applying desired dressing daily to affected areas and securing with tape as needed. Participants may change dressings as needed. Instructions will be reviewed with participants upon enrollment. Participating subjects will also be given a 2-week log where they will be instructed to fill in which dressings they used on which wounds, and how often they changed the dressings.

Subjects will receive weekly phone calls in between follow ups (for a total of 4 phone calls) by the research team where they will be asked to answer questions on average and maximal pain, quality of sleep, drainage and odor. Subjects will be asked to follow up in 14 +/- 3 days from visit 0 (visit 1), at which point the physical exam will be performed. Maximal and average pain will again be assessed on a 5-point likert scale. Quality of sleep, drainage, and odor will be assessed as well (Table 1). Photographs and measurements of HS wounds will be taken and the dressing logs will be collected and evaluated. Wound swab samples will be collected from the wound that was pre-identified at baseline visit. Participants will share with study personnel which dressings were most useful to them, and this will dictate the dressing type that each subject receives for the remaining 4 weeks of the study period.

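### Eligibility does not screen for known sensitivity to the study dressings or tape, although contact dermatitis is the only dressing risk named, and the risk comparison is unsupported for sensitized subjects

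*Combined protocol and SAP*

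**What the plan says.** **Risk.** The closing paragraph of 8.3 (SAE reporting), within the Adverse Events section, states: "Risks to subjects in this study include contact dermatitis in the skin areas exposed to the dressings provided in this study". It then argues that the dressings, being FDA-cleared and marketed, "pose a risk that is no higher than the current risk subjects are undertaking while utilizing other dressings over the same skin areas".

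**Eligibility.** Section 3 has four exclusions: "Subjects younger than 18-years-old", prisoners, "Pregnant or lactating women", and "Adults unable to consent". The inclusion list asks for adult age, a dermatologist's diagnosis of hidradenitis suppurativa, consent, and "Presence of at least one lesion with active drainage". Section 9 (Vulnerable Populations) repeats the exclusion of pregnant women, prisoners and children and adds nothing on sensitivity.

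**Exposure.** Under section 4 each subject receives a kit of three named dressings together with "general wound care supplies (i.e. tape, gauze) that are also FDA-cleared and available on the market". On use, it says: "Dressing instructions involve applying desired dressing daily to affected areas and securing with tape as needed".

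**The concern.** The protocol names a hazard and then does not screen for the people in whom it is most foreseeable. A candidate with a documented contact allergy to one of the dressings, or to the tape, passes every criterion and goes home with the item.

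The reassurance in 8.3 does not close this gap. Clearance and market availability describe a product. They do not show that risk is unchanged for an individual already known to react to it, whose present dressing may have been chosen because it is tolerated.

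What is at stake is an avoidable skin reaction in areas that are already inflamed and draining, and a risk statement that does not fit every eligible subject.

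**Working it through.** No figure in the documents tests this point, so the check is a reading of every place that could deal with known sensitivity. The sample-size figures in section 14 (30 enrolled to reach 20) play no part in it.

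**Step 1. Is there a screen for sensitivity?**

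| Place | What it provides | Does it screen for known sensitivity? |
|---|---|---|
| Section 3, inclusion | Age, diagnosis, draining lesion, consent | No |
| Section 3, exclusion | Four entries, none tied to the intervention's named risk | No |
| Section 9 | Repeats three of the excluded groups | No |
| Table 1, note A | Disease history with current wound care and exacerbating factors | No: allergy is not named and no answer affects eligibility |
| 8.1, conditions present at consent | Recorded in the medical history | No: recording only |
| Section 4, instructions | Reviewed with the subject at enrolment | No: no sensitivity check is described |
| 8.1, action after an adverse event | Dressings may be interrupted or withdrawn | No: acts only after a reaction |
| 8.2 | Allergic bronchospasm, as a generic example of a serious event | No |

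A person with a known sensitivity to a kit item is therefore eligible as written.

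**Step 2. How soon would a reaction be found?** After baseline there are 4 phone calls and 2 visits, 6 contacts in all. Table 1 schedules adverse event assessment at 2 of the 6: Visit 1 (about Day 14) and Visit 2 (up to Day 42). Section 4 describes the calls as covering pain, sleep, drainage and odor. Under 8.1 subjects may volunteer events between visits, so earlier detection is possible but depends on the subject.

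**Step 3. Does the comparison in 8.3 hold for a sensitized subject?** It sets the study dressings against the dressings the subject uses now. The answer depends on the case:

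- Sensitized to a study dressing, uses it, and does not meet the sensitizer in current care: the comparison fails.
- Sensitized, but already exposed to the same material in current care: it need not fail.
- Sensitized to one dressing, but uses another from the kit: it need not fail.
- Sensitive to the tape: the sentence compares dressings only and is silent.

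The documents give neither the composition of the dressings nor any reaction rate, so they cannot tell these cases apart. The comparison is unsupported for this group, and the text goes no further than that.

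**The case against.** The best case on the other side is that eligibility is not exposure. Subjects apply the dressing they want, use tape only as needed, and may change dressings as they see fit. Nothing obliges anyone to try all three. A subject who knows of a sensitivity is well placed to avoid the item. A dermatologist with wound expertise leads the study, history is taken at baseline, and dressings can be stopped after a reaction. The consent form is not in the supplied text and may carry an allergy warning.

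Much of this stands as mitigation, but none of it is an eligibility check. Avoidance works only if the subject can connect the sensitivity to a particular item, and the study invites subjects to find out which dressings serve them best. A consent warning, if there is one, would not change section 3.

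It can also be said that intolerance of one item does not make a kit of choices useless, and that excluding the whole person narrows a deliberately broad pilot population. That is fair, and it belongs in the cost of the fix.

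A reader might go further and infer three things that the documents do not support:

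- **That the risk comparison is false for sensitized subjects.** Step 3 of the check shows that it fails in one case, need not fail in two others, and does not address tape.
- **That reactions would materially shift the primary endpoint.** The documents give no prevalence of sensitivity and no size of effect on DLQI. DLQI is taken only at baseline and at the end of treatment. The dressings a subject reports as most useful at Visit 1 determine what is supplied for the last 4 weeks, so an early reaction would tend to steer the subject away from the cause before DLQI is measured again.
- **That dressing preference would be biased.** Disliking a dressing because it caused a reaction is a legitimate preference, and preference is one of the study's outcomes.

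**Conclusion.** The point holds as a gap in eligibility and in the wording of the risk statement. Section 3 admits people with a known sensitivity to an item in the kit, while 8.3 names contact dermatitis as the only specific dressing risk. The wording there leaves room for other risks, so it is the only one named and not necessarily the only one contemplated. The comparison with current dressings is unsupported for sensitized subjects, not shown to be untrue.

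No size can be put on it from the documents, and the conclusion does not need one. It rests on the text of sections 3, 4 and 8.3 and on the absence of a screen elsewhere in the supplied text. The case is avoidable safety risk, and the very low cost of removing it makes the change worth making.

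**What to change.** 1. Add to the exclusion criteria in section 3: *Known allergy or contact sensitivity to any component of the three study dressings or the supplied tape.*
2. Check it at the Visit 0 Inclusion/Exclusion Determination in Table 1, from the history taken at that same visit, with allergy and contact sensitivity asked about explicitly.
3. In the risk paragraph of 8.3, limit the comparison with current dressings to subjects without such a history.

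The cost is one exclusion line, one history question and one qualifying phrase, with no added visit or procedure. The downside is that a few candidates may be lost and the results would reach adhesive-sensitive patients slightly less.
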